## **Scientific Protocol**

**Title:** Effects of Device-Facilitated Isometric Progressive Resistance Oropharyngeal (I-PRO) Therapy on Dysphagia Related Outcomes in Patients Post-stroke

**Principal Investigator:** [name], CCC-SLP

**Institution:** University of Wisconsin-Madison

**Co-Investigators:** [name]

**Protocol Version Date:** 07-07-2015

**Funding Sponsor:** This study is funded by an American Speech-Language-Hearing Foundation (ASHFoundation) New Investigator grant.

**Project Summary:** The overall goal of this randomized controlled pilot study is to characterize effects of SwallowSTRONG® Device-Facilitated Isometric Progressive Resistance Oropharyngeal (DF I-PRO) therapy in a dose response framework on swallowing-related outcomes in a group of unilateral ischemic stroke patients. These results will be used to determine adequate sample size in order to support a larger clinical trial focused on the efficacy of this therapy approach for improving swallowing safety. The first aim is to determine differences in swallowing physiology and bolus flow measures a) between a group of unilateral ischemic stroke subjects undergoing SwallowSTRONG® DF I-PRO therapy and controls and b) between 8 and 12 weeks of treatment. The second aim is to examine changes in level of oral intake and swallowing quality of life in post-stroke patients undergoing DF I-PRO therapy as compared to a control group and as they relate to treatment duration response at 8 weeks and 12 weeks. The third aim is to evaluate effects of DF I-PRO therapy on overall health status reflected by the number of pneumonia diagnoses and overall hospital readmission rates in post-stroke subjects undergoing DF I-PRO therapy compared to controls.

## **Background and Significance**

**Prevalence:** Every 40 seconds, on average, someone in the United States experiences a stroke.

Due to the advancing age of the US population, by 2030, an estimated four million additional people will have had a stroke, a 21.9% increase in prevalence from 2013. Dysphagia is estimated in up to 76% of acute stroke patients and is known to increase the risk for critical post-stroke health sequelae, including pneumonia, malnutrition, dehydration, and mortality.

**Complications:** Developing pneumonia post-stroke results in a significantly increased relative risk (2.99) of death within 30 days of hospital discharge. Those patients who experience aspiration are *seven* times more likely to develop pneumonia than those who do not aspirate. Relatedly, patients with dysphagia following stroke experience significant decreases in quality of life, increased eating dependency, diminished rehabilitation potential, and longer hospital stays.

**Swallowing physiology:** Videofluoroscopic findings in patients post-stroke include poor tongue control, increased bolus transit times, reduced laryngeal closure duration, decreased and/or incomplete laryngeal elevation, and higher (worse) penetration-aspiration scale scores compared to controls. Sensory deficits also are common following stroke leading to silent aspiration. Oral sensory deficits also may occur making it difficult for a patient safely to control the bolus or to initiate a swallow.

**Tongue strength:** Swallowing consists of a series of pressure changes that begin at the lips and the muscular tongue is a major propulsive force during the swallow. Pressures produced when the tongue contacts the palate play a critical role moving the bolus through the oropharynx and into the esophagus. Patients with dysphagia post-stroke have lower average maximal isometric tongue pressures than those without dysphagia. Tongue pressure production has been found to be closely related to post-stroke dysphagia.

**Age effects:** The vast majority of all strokes occur in people over age 65. Healthy older adults swallow more slowly and generate lower maximum isometric lingual pressures than younger controls. These reductions in strength are likely due, at least in part, to the effects of sarcopenia, age-related skeletal muscle loss of the head and neck musculature. Swallowing pressure reserve, the difference between isometric (maximal) tongue pressures and tongue pressures during swallowing (submaximal), is reduced with age which places older adults at higher risk for dysphagia following additional insult, such as stroke. Kays et al studied the effects of consuming an entire meal on tongue endurance in healthy young and old adults and results indicate that both groups experience reduction in tongue strength and endurance post-meal. Older adults perceived increased effort and fatigue upon completing a meal and coughing or throat clearing later in the meal, suggesting airway invasion. These results reflect that the act of dining decreases tongue strength and tongue endurance with potentially harmful effects (aspiration) in older healthy individuals. Such findings have great implications for dysphagic stroke patients who already demonstrate impairments in tongue strength.

**Swallowing Interventions in Patients Post-stroke:** Traditionally, interventions to improve swallowing in elderly patients are focused on energy conservation and are largely compensatory in nature minimizing the need for intense activity. Postural adjustments, such as a chin tuck or head turn, are frequently recommended in order to modify bolus flow. Diet modifications, such as withholding thin liquids or restricting liquid intake to thickened liquids, are commonly used in hospitals and long-term care facilities to minimize or eliminate thin liquid aspiration. Evidence for these approaches is limited. In addition, these practices may negatively affect health

status, particularly the recommendation of honey-thickened liquids. They also affect quality of life and fail to capitalize on the neural basis of recovery post-stroke. Finally, these techniques require use with each swallow which may be disruptive to the eating process and difficult to maintain.

**Resistance Training and Swallowing:** Past assumptions that the swallowing process is a function of the reflexive neural underpinnings and is not responsive to voluntary modification have been proven incorrect through studies reporting the occurrence of dysphagia following, not only brainstem stroke, but also bilateral and unilateral cortical stroke. Now considered a patterned sensorimotor process or response within a complex neural network involving both automatic and volitional systems that respond to sensory inputs, swallow function is amenable to restoration. Intensive, repetitive strengthening that results in central neuroplastic modifications as well as peripheral increases in muscle mass and strength has been found to substantially improve swallow muscle physiology and functional outcomes related to swallow behavior.

Effects of sarcopenia that occur with aging in striated musculature have been shown to be largely reversible through studies of healthy older adults. Eight weeks of progressive resistance training by frail elders has been associated with increased gait speed, activity level, stair climbing and diminished risk for falls. In addition, stroke subjects who complete a strengthening regimen for the extremities have shown improvements in functional activities such as timed stair climbing, walking and chair rising. Progressive resistance strength training can be defined as progressive increases in resistance to a muscle or group of muscles as training results in greater ability to create and maintain forces.

Just as participation in progressive resistance training can strengthen striated limb musculature to improve mobility, it also benefits bulbar-innervated striated muscles of the head and neck. A recent study of community-dwelling individuals aged 70 years and older demonstrated positive correlations between isometric tongue pressure and grip strength and jump height. These data support the effects of sarcopenia on the head and neck musculature and consideration of oropharyngeal functional decline as part of the sarcopenia syndrome. Results of a study by Robbins et al demonstrated positive changes in lingual isometric and swallowing strength of healthy adults over 70 years of age following progressive isometric resistance (high intensity, repetitive, non-specific) exercises for the tongue and related musculature using the Iowa Oral Performance Instrument (IOPI). In 2007, Robbins et al used the same approach with ten patients post-stroke. Subjects demonstrated statistically significant changes in isometric tongue strength as well as pressures generated by the tongue during swallowing, indicating carryover into functional activity. Aspiration and oropharyngeal residue were reduced with liquids in these stroke subjects; and a subset of subjects demonstrated an increase in tongue volume as measured by magnetic resonance imaging implying enhanced tongue muscle mass.

**Device-facilitated I-PRO therapy:** Device-facilitated (DF) Isometric Progressive Resistance Oropharyngeal (I-PRO) therapy is an approach to oropharyngeal strengthening based on core principles of exercise physiology derived from the sports medicine literature. At the start of therapy, the patient's one repetition maximum, or the maximum amount of pressure s/he can produce with the tongue against the palate, is calculated. Then, the patient is instructed to press against a sensor located along the palate at 60 to 80% of that maximum. Therapy involves pressing the tongue against each sensor ten times, three times per day, and three days per week for eight weeks. Maximum pressures are re-determined every 2 weeks to progress therapy targets as patients become stronger.

Existing studies of DF I-PRO therapy showing improved swallow function have utilized the IOPI, which comprises a single air-filled plastic bulb attached to a hand-held pressure transducer. The smooth plastic bulb may slide in the oral cavity as patients apply pressure and may cause varying pressure readings due to inconsistent placement. In contrast, the Madison Oral Strengthening Therapeutic (MOST®) device 1.0 (Swallow Solutions LLC, Madison, WI, USA) has an intraoral mouthpiece that comprises 5 air-filled sensors that independently target the anterior, posterior, left, right, and middle tongue. This mouthpiece is custom-fit to the hard palate, registers to the anterior upper dentition or alveolar ridge, facilitating consistent placement over time. The MOST® device recently has undergone its second iteration which uses a touch screen tablet and is now referred to as the SwallowSTRONG® device.

A federally-funded Clinical Demonstration Program, the Swallow STRengthening OropharNGeal (Swallow STRONG) program, has shown positive results for a group of 40 Veterans with oropharyngeal dysphagia resulting from a variety of medical etiologies including stroke. Veterans underwent 8 weeks of MOST® DF I-PRO therapy and were assessed at baseline prior to beginning the program as well as following completion. Maximum isometric pressures were found to increase significantly at the front and back sensors ( $p<.001$ ) selected for the regimen. Decreases were observed in penetration-aspiration scale scores for 3ml and 5ml thin liquid boluses. Scores on the eating desire, physical, fear, social, fatigue, and mental health subscales of the Swallowing Quality of Life (SWAL-QOL) questionnaire improved ( $p<.03$ ). Ratings of effort with swallowing decreased ( $p<.01$ ) as did ratings for the statement “Food sticks in my mouth when eating” ( $p<.01$ ). Functional Oral Intake Scale (FOIS) scores improved significantly ( $p<.02$ ), representing progression from feeding tube dependency to full oral intake. For patients who could be tracked 6 months or longer following enrollment, the number of pneumonia diagnoses decreased by 88% and hospital admissions decreased by 79%.

This initial work supports the potential of this therapy approach to affect health-related outcomes in addition to swallowing-specific outcomes in a variety of patient groups. However, the efficacy of SwallowSTRONG® DF I-PRO therapy for treating dysphagia and overall health status in patients post-stroke has yet to be established in a larger, more homogeneous group of subjects and with comparison to a control group.

*Salivary Analyses:* A decrease in ratings of mouth dryness has also been observed in patients enrolled in the VA Clinical Demonstration Program previously referred to. The reason for this decrease in mouth dryness is unclear. Additionally, levels of substance P, a protein in saliva, have been shown to be related to the occurrence of silent aspiration in patients post-stroke. Some preliminary data have shown that intraoral stimulation may increase levels of substance P. Stimulation of the salivary glands provided by repeated lingual presses may have the same outcome. Analyses of salivary flow rate as well as the quality of saliva will be important in more clearly understanding these observed changes in this group of patients post-stroke.

*Dose Response:* In order to encourage optimal outcomes of SwallowSTRONG® DF I-PRO therapy, while simultaneously considering patient tolerance and compliance, knowledge of ideal treatment duration is critical. In previous work, DF I-PRO therapy has been implemented as an 8 week program; however, acute and chronic post-stroke patients have continued to demonstrate improvement at completion of the program. This suggests that a subset of patients may benefit from a longer protocol (dose).

## **Specific Aims**

This randomized controlled pilot study will characterize effects of SwallowSTRONG® Device-Facilitated Isometric Progressive Resistance Oropharyngeal (DF I-PRO) therapy in a dose response framework on swallowing-related outcomes in a group of unilateral ischemic stroke patients. These results will be used to determine adequate sample size in order to support a larger clinical trial focused on the efficacy of this therapy approach for improving swallowing safety. This randomized study will expand upon previous work examining effects of this therapy approach on swallowing and health-related outcomes now limited to a heterogenous cohort of Veterans with dysphagia from a variety of etiologies. It will focus specifically on patients post-stroke who have been shown to experience improvements in swallow function following DF I-PRO therapy.

**Specific Aim 1:** To determine differences in swallowing physiology and bolus flow measures a) between a group of unilateral ischemic stroke subjects undergoing SwallowSTRONG® DF I-PRO therapy and controls and b) between 8 and 12 weeks of treatment.

**Hypothesis 1a:** Subjects treated with DF I-PRO therapy at both treatment duration points will demonstrate greater improvements in swallow physiology (isometric and swallowing pressures) as well as bolus flow measures (levels of airway invasion, post-swallow residue/stasis, oral transit times, and stage transition duration times) as compared to the control group.

**Hypothesis 1b:** Subjects treated with DF I-PRO therapy will experience improvements in swallow physiology and bolus flow measures at the 12 week duration compared to 8 weeks.

**Specific Aim 2:** To examine changes in level of oral intake and swallowing quality of life in post-stroke patients undergoing DF I-PRO therapy as compared to a control group and as they relate to treatment duration response at 8 weeks and 12 weeks

**Hypothesis 2a:** Patients undergoing DF I-PRO therapy will require less restrictive diets and will report improved swallowing-related quality of life compared to those in the control group at both treatment duration points.

**Hypothesis 2b:** Twelve weeks of DF I-PRO therapy will result in greater improvements (least restrictive diets and improved quality of life) compared to the 8 week duration.

**Specific Aim 3:** To evaluate effects of DF I-PRO therapy on overall health status reflected by the number of pneumonia diagnoses and overall hospital readmission rates in post-stroke subjects undergoing DF I-PRO therapy compared to controls.

**Hypothesis 3a:** There will be a greater decrease from pre- to post-enrollment in the number of pneumonia diagnoses and overall hospital readmissions for those subjects who complete 12 weeks of DF I-PRO therapy compared to controls.

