## **Intervention**

Participants who meet criteria for dysphagia on the videofluoroscopic swallowing examination will be randomly assigned into one of two groups: 1) a control group that will be receiving compensatory treatments only or 2) 12-week DF I-PRO therapy *plus* compensatory treatments, such as thickened liquids and/or postural strategies during natural swallowing activities for 12 weeks. Patients will be enrolled and trained in DF I-PRO therapy by [name] who regularly uses the SwallowSTRONG®-facilitated I-PRO therapy in clinical practice or a UW Voice and Swallowing clinician involved in this study who has been adequately trained in DF I-PRO therapy. Regardless of the treatment group to which a subject is randomized, they will be evaluated in the hospital at baseline and 8-week time points. If a patient in either group no longer meets criteria for dysphagia (Penetration-Aspiration Scale score of 3 or higher OR a rating of 2 on the Residue scale in any location) on the 8-week videofluoroscopic swallowing examination, s/he will no longer continue participation in the study. If a patient in either group remains dysphagic at the 8-week visit, s/he will continue participation in the study through the 12-week assessment point. [name] or a UW Voice and Swallowing clinician will conduct the 8 and 12 week assessments.

**Group 1: Compensatory treatments only:** This group will receive standard swallowing intervention, which is identified by the SLP as appropriate to treat the patient's dysphagia and is common clinical practice. This group is not receiving experimental therapy. Their therapy may include: 1) modifying the foods the subject eats or the fluids s/he drinks; 2) changing his/her posture when eating or drinking (for example, by a simple chin tuck) or using a swallowing maneuver while eating or drinking; 3) having him/her eat more slowly or in a quiet environment to make swallowing easier and safer; or 4) performing range of motion or vocal exercises for

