**Figure 1**

## **Visits**

**Baseline visit only:**

After the informed consent process has been completed but prior to videofluoroscopic examination of swallowing, each participant will complete a medical history questionnaire to ensure they meet inclusion/exclusion criteria. This questionnaire will include items related to current medical status, medical history, and medication usage. UW medical records also will be referenced to ensure the subject's eligibility for participation. As part of this screening, patients will undergo a urine pregnancy test to ensure they are not pregnant prior to participation. The Mini-Mental Status Examination (MMSE) will be administered only at baseline as a common examination of cognitive functioning. In addition, the Barthel index will be administered to assess severity of impairments in activities of daily living. For each patient, a form with demographics as well as a medication list will be filled out. These questionnaires and tests will take approximately 45 minutes to complete. For those subjects randomly assigned to Group 2, during this baseline visit, it also will take approximately 30 minutes to train the participant on how to do and record the exercises properly. In addition to the consent process and these procedures that will occur only at the baseline visit, the procedures described below will also be completed at this visit. The entire baseline visit will last about 2.5 hours. For the baseline visit and 8 week visit, videofluoroscopic examination of swallowing will need to be completed before the other procedures outline below as the outcome of that examination will determine the patient's continued participation in the study. If s/he does not meet criteria for dysphagia on the videofluoroscopic swallowing exam, s/he will either not be randomized to a study group (at baseline visit) or will not continue participation past the 8 week point (if dysphagia has resolved).

*Measures at each assessment point (baseline, 8 weeks, and 12 weeks):* The 8 week and 12 week visits will last about 90 minutes per session. The study includes up to 3 sessions which will require up to 7 hours in total. In addition if in Group 2, participation in the home exercises will last about 10 minutes per session, 9 sessions per week for up to 12 weeks, which will require up to 18 hours total.

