### **Data Reduction and Analysis**

*Videofluoroscopic Analysis:* The videofluoroscopic images will be coded and sent to the Speech Swallowing And Dining Enhancement (SSwal-ADE) Program. Clinicians blinded to subject information will obtain measures of bolus flow kinematics-direction (Penetration/Aspiration Scale scores), duration, and completeness (Residue Scale scores) from fluoroscopic recordings for each subject using Adobe Premier Pro software. Visual perceptual review will be performed by judges viewing each swallow at normal, slowed, and frame-by-frame speeds as often as needed for confident judgments. Twenty percent of the swallows will be chosen randomly and re-measured by the same judge and a different judge (one of the experienced UW SLPs) to assess inter and intra-judge reliability for all variables. Bolus flow durational measurements (oral transit time, stage transit duration, pharyngeal transit time, total swallow duration) will quantify timing of structural movement and bolus flow. *Computational analysis of swallowing mechanism (CASM) will be performed in order to track anatomical coordinates during the swallow. This will allow us to quantify displacement of various swallowing related structures.*

*Pressure Analysis:* Maximum isometric and swallowing pressures and their temporal characteristics (i.e., rise rate) will be quantified using the SwallowSTRONG® device and the DSW. Swallowing pressures will be quantified relative to the videofluoroscopic images to ensure that the pressure being measured is relevant to bolus flow and not bolus manipulation prior to the swallow. Twenty percent of the pressure wave forms will be chosen randomly and re-measured by the same judge and a different judge to assess inter- and intra-judge reliability.

*Swal-QOL:* Responses will be extracted and scored for subsequent statistical analysis using a database scoring program. All of the Swal-QOL scales will be scored by using Likert's methods of summated ratings.

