## **Statistical Analyses**

Prior to data analyses, the data collected under this study will be combined with data from its VA counterpart (IRB #2014-0939). Statistical analyses will be performed using this combined data set.

**Aim 1:** A repeated measures analysis model will be used to model changes in tongue strength in treatment and control groups, adjusted for age, gender, and baseline tongue strength. Each subject will have three observations: change between baseline and 8 weeks, baseline and 12

weeks, and 8 weeks and 12 weeks. This model will allow for comparison of differences between a) treatment durations (dose response) and b) between control and treatment groups.

**Aim 2:** Changes in oral intake and swallowing quality of life between baseline and 8 weeks, baseline and 12 weeks, and 8 weeks and 12 weeks will be modelled in a repeated measures analysis on treatment, adjusting for age, gender, and baseline outcome.

**Aim 3:** Change in number of new pneumonia diagnoses and number of hospital readmissions over a 1 year period, pre and post-study, will be modelled in linear regression models on treatment, adjusting for age, gender, and pre-study outcome.

All analyses will be performed on a randomized, or intention to treat basis, regardless of the actual treatment received. Study dropout by the subject will result in inclusion of incomplete data for that patient.

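### Week-12 exams exist only for subjects who still fail the week-8 swallow study, so the 8-to-12-week change in airway invasion and residue under Hypothesis 1b leans toward improvement even with no real change

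*Combined protocol and SAP*

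**What the plan says.** **The gate.** The Intervention section defines dysphagia as "Penetration-Aspiration Scale score of 3 or higher OR a rating of 2 on the Residue scale in any location". A subject in either group who no longer meets this "on the 8-week videofluoroscopic swallowing examination, s/he will no longer continue participation in the study". For the rest: "If a patient in either group remains dysphagic at the 8-week visit, s/he will continue participation in the study through the 12-week assessment point". The Visits section repeats the rule: a subject "will not continue participation past the 8 week point (if dysphagia has resolved".

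**The outcome.** Hypothesis 1a, under Specific Aims, lists "bolus flow measures (levels of airway invasion, post-swallow residue/stasis, oral transit times, and stage transition duration times". Data Reduction and Analysis scores the first two with the Penetration-Aspiration and Residue scales, read from the videofluoroscopic recordings: "Clinicians blinded to subject information will obtain measures of bolus flow kinematics-direction".

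**The contrast.** Hypothesis 1b says that treated subjects "will experience improvements in swallow physiology and bolus flow measures at the 12 week duration compared to 8 weeks". Unlike Hypothesis 1a, it names no control group.

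**The analysis.** The Aim 1 paragraph of Statistical Analyses describes a repeated measures model of change in tongue strength in both groups, with the 8-to-12-week change as one of three observations per subject. It adds: "This model will allow for comparison of differences between a) treatment durations (dose response". No model is written for airway invasion or residue. The section promises intention-to-treat analysis and says that incomplete data from dropouts are included. It does not mention subjects who leave at week 8 because the protocol requires it.

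**The concern.** The scores that admit a subject to week 12 are also the starting values of the change that Hypothesis 1b interprets. Part of any failing week-8 exam is exam-to-exam variation. Subjects chosen for a bad reading will on average read better next time, even if their swallowing is perfectly stable. This is separate from natural recovery after stroke, and it operates with no true change at all.

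The direction matters because the pilot is meant to inform treatment duration and to size a larger trial. An apparent gain between weeks 8 and 12 would favour the longer programme. Meanwhile the treated subjects who resolved by week 8, who are evidence that eight weeks may suffice, have no week-12 exam.

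**Working it through.** **The plan's own figures.** The documents give no figure for this point. Their only power calculation is for tongue pressure. It reproduces (noncentral t, 15 per group, SD 100 hPa, difference 80 hPa, two-sided 0.05: 56.2% against the stated 56%) but has no bearing here.

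**Inputs from the documents.** The week-8 gate; 15 subjects per group (Sample size calculation); alpha 0.05 (Table 2).

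**Assumed inputs.** Scores roughly normal with SD 1 at week 8; no true change from week 8 to week 12; week-8/week-12 correlation *r* of 0.5 to 0.8; fraction *q* of treated subjects continuing of 0.4 to 0.6. The documents give neither *r* nor *q*.

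**Single-score gate.** Let *z* be the normal cut-point that leaves fraction *q* above it.

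- Mean excess of continuers at week 8: m = φ(z)/q
- Expected spurious gain: m(1 − r)
- Variance of the selected scores: V = 1 + zm − m²
- Variance of the change: (1 − r)²V + (1 − r²)
- Chance of a significant improvement: upper tail of a noncentral t with n = 15q (rounded), two-sided 0.05

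Worked case, q = 0.5 and r = 0.5: z = 0; m = 0.399/0.5 = 0.798; gain = 0.798 × 0.5 = 0.40 SD. V = 1 − 0.637 = 0.363. Variance of change = 0.25 × 0.363 + 0.75 = 0.841. With n = 8 the noncentrality is (0.399/√0.841) × √8 = 1.23, and the chance is 19%.

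| q | m | Gain, r = 0.5 to 0.8 | Chance of false improvement (nominal 2.5%) |
|---|---|---|---|
| 0.4 | 0.966 | 0.48 to 0.19 SD | 19% to 9% |
| 0.5 | 0.798 | 0.40 to 0.16 SD | 19% to 9% |
| 0.6 | 0.644 | 0.32 to 0.13 SD | 15% to 8% |
| 0.9 | 0.195 | 0.10 to 0.04 SD | about 5% to 4% |

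**Either/or gate.** The real rule admits a subject who fails on either score, so someone admitted on residue was not selected on airway invasion. I simulated two scores with an assumed correlation of 0.3 and the same ranges of *r* and *q* (0.4 to 0.6). The gain per score falls to about 0.09 to 0.35 SD and the false-improvement rate to about 6% to 11%; a repeat run put the upper end at 12%.

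**Comparison with controls.** Controls pass the same gate. In simulation with equal gating in both arms, a between-arm test of the 8-to-12-week change among continuers stays at about 5% two-sided. With a single-score gate, a likelihood-type estimate that keeps week-8 scores from all subjects cuts the bias in the treated-group change to about 0.00 to 0.04 SD.

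**The case against.** The best defence is that the plan nowhere specifies a paired, treated-only test. The Aim 1 model contains both groups and names only tongue strength, and the Outcomes section lists neither Penetration-Aspiration nor Residue scores. Exit depends on an observed exam, so a likelihood-based model that includes incomplete data could remove most of the bias. The gate may also be decided on the clinic reading while the outcome comes from a separate blinded reading; if so, error by the first reader does not carry into the outcome.

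Much of this limits the size and reach of the point, but it does not remove it. Hypothesis 1b is still worded as a gain within treated subjects, and the plan does not say that its model is likelihood-based or how week-8 leavers enter it. Separate readings would remove only reader error, not the variation of the swallow itself from one exam to the next. Cancellation against controls needs similar exit rates, which would differ if treatment works.

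Three stronger readings are tempting and are not supported:

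- *The plan will report a false gain.* Even on the single-score figures, 81% to 92% of such trials would show no significant improvement.
- *The duration comparison fails for every outcome.* Tongue pressure is measured by the device and is not a gating variable. The transit and transition times are touched only through their correlation with the gating scores.
- *Subjects resolved at week 8 contribute nothing.* They have no 8-to-12-week change, but the incomplete-data sentence leaves room for a model that uses their earlier visits.

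**Conclusion.** The point holds for airway invasion and residue. Their 8-to-12-week change within treated subjects is biased toward improvement whenever some subjects leave at week 8 and retest correlation is below 1. Nothing in Statistical Analyses clearly corrects this.

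The direction follows from the documents; the size does not. It rests on assumed retest correlation, continuing fraction, normality and, for the either/or gate, the correlation between scores. The either/or range is closer to the plan's rule than the single-score range, and both are illustrative because the scores are graded scales. If nearly all subjects remain dysphagic at week 8, the effect is close to negligible.

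This is a correction to one stated hypothesis in a pilot. It does not directly touch the primary outcome.

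**What to change.** 1. In Hypothesis 1b and Aim 1, remove airway invasion and residue from the within-treated 8-versus-12-week claim.
2. Report the 8-to-12-week change in these scores among continuers descriptively, stating that improvement is expected from selection alone.
3. Base any inference on them on a treatment-minus-control contrast from a likelihood-based repeated measures model. Model the scores at each visit rather than the changes, and keep baseline and week-8 scores of all randomised subjects, including those who left at week 8. Because exit depends on both scores, the model should use both.
4. Optionally, add the proportion free of dysphagia by week 12 (resolved at week 8, or below both thresholds at week 12) as a between-arm risk difference with 95% CI. State three limits. It assumes that early leavers stay resolved. Passing at either exam raises the rate by chance in both arms (in simulation with stable swallowing and half continuing, from 50% to about 61% to 68%). It does not answer the 8-versus-12-week question.

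The cost is wording and analysis of data already collected; the visit schedule and the exit rule are unchanged. The uncontrolled duration test of these two scores is given up. Between-arm estimates will be imprecise: at 50% in each arm of 15, the risk difference has a 95% half-width of about 1.96 × √(2 × 0.25/15) = 0.36.
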